Blood sample for viral characterization ^l	X															
Blood sample for storage for immune status ^m	X		X		X	X		X				X	X	X	X	X
MMSE ⁿ	X					X		X		X		X	X	X	X	
CDR ⁿ	X				X	X	X	X	X	X	X	X	X	X	X	

Table 3 Schedule of Procedures/Assessments in Study E2609-G000-302

Phase Period	Randomization															ED ^b	Follow-Up		UNS Visit ^d
	Treatment												14 ^c	15 ^c					
Visit ^a	2	3	4	5	6	7	8	9	10	11	12	13		14 ^c	15 ^c				
Day	1	15	29	57	85	183	274	365	456	547	638	729		757	813				
Week	1	3	5	9	13	27	40	53	66	79	92	105		109	117				
Weeks elapsed since 1st dose	0	2	4	8	12	26	39	52	65	78	91	104		108	116				
Nominal months elapsed since 1st dose	0		1	2	3	6	9	12	15	18	21	24		25	27				
Procedures/ Assessments																			
ADAS-cog ₁₄ ⁿ	X					X		X		X		X	X	X	X				
FAQ ⁿ	X					X		X		X		X	X	X	X				
Disease Staging ^o					X	X	X	X	X	X	X	X	X		X				
NPI ₁₀	X					X		X		X		X	X		X				
C-SSRS	X											X	X						
Clinical assessment of suicidal thinking and behavior ^p		X	X	X	X	X	X	X	X	X	X			X	X	X			
EQ-5D ^q						X		X		X		X	X						
QOL-AD ^r						X		X		X		X	X						
Zarit's Burden Interview of study partner						X		X		X		X	X						
MRI including vMRI and fMRI ^s								X				X	X						
Amyloid PET (optional substudy) ^t								X				X	X						
Telephone contact ^u		X	X		X	X		X		X		X	X						
Blood samples for PK ^v		X	X		X	X		X		X		X	X						
Blood samples for PD and other biomarkers ^w		X	X		X	X		X		X		X	X	X	X				
CSF sampling for PK and PD (optional substudy) ^x												X	X						
Adverse events	X	X	X	X	X	X	X	X	X	X	X	X	X	X	X	X			

Table 3 Schedule of Procedures/Assessments in Study E2609-G000-302

Phase Period	Randomization														Follow-Up		UNS Visit ^d
	Treatment												ED ^b	14 ^c	15 ^c		
Visit ^a	2	3	4	5	6	7	8	9	10	11	12	13					
Day	1	15	29	57	85	183	274	365	456	547	638	729		757	813		
Week	1	3	5	9	13	27	40	53	66	79	92	105		109	117		
Weeks elapsed since 1st dose	0	2	4	8	12	26	39	52	65	78	91	104		108	116		
Nominal months elapsed since 1st dose	0		1	2	3	6	9	12	15	18	21	24		25	27		
Procedures/ Assessments																	
Sleep/Dream Questionnaire ^y	X	X	X	X	X	X	X	X	X	X	X	X	X	X	X	X	
Possible Drug Abuse Potential Form/ Questionnaire ^z	X	X	X	X	X	X	X	X	X	X	X	X	X	X	X	X	
Randomization	X																
Dispense study drug	X ^{aa}	X	X	X	X	X	X	X	X	X	X						

Notes

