ADAS-cog₁₄ = Alzheimer’s Disease Assessment Scale - Cognitive subscale (14 items), CBP = child-bearing potential, CDR = Clinical Dementia Rating scale, CMV = cytomegalovirus, CNS = central nervous system, CSF = cerebrospinal fluid, C-SSRS = Columbia Suicide Severity Rating Scale, ECG = electrocardiogram, ED = Early Discontinuation, EQ-5D = EuroQol-5 Dimensions, FAQ = Functional Assessment Questionnaire (also known as the Functional Activities Questionnaire), fMRI = functional MRI (to be performed task free at resting state), HSV1 = herpes simplex virus 1 (orolabial herpes), HSV2 = herpes simplex virus 2 (genital herpes), INR = International Normalized Ratio, LP = lumbar puncture, MMSE = Mini Mental State Examination, MRI = magnetic resonance imaging, NPI = Neuropsychiatric Inventory, PBMC = peripheral blood mononuclear cell, PD = pharmacodynamics, PET = positron emission tomography, PK = pharmacokinetics, QOL-AD = Quality of Life in Alzheimer’s Disease, UNS = unscheduled, vMRI = volumetric MRI.

^a A window of ±3 days will be permitted for Visits 3 and 4. A window of ±7 days will be permitted for Visits 5 and 6. A window of ±10 days will be permitted for Visit 7 to 13 inclusive. A window of ±3 days will be permitted for the Follow-Up Visits. If use is made of the permitted visit windows, every effort should be made to bring the subject back in line with the “weeks elapsed since 1st dose” at subsequent visits.

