^b Subjects who discontinue taking study drug prematurely for any reason will undergo an ED Visit within 7 days of their last dose of study drug. In addition, Follow-Up Visits will be scheduled 4 and 12 weeks after the last dose of study drug (Visit 14 and Visit 15, respectively). Subjects who discontinue study drug before reaching 12 months of treatment will also be asked to return to the clinic for a 12 month clinical assessment and then again at 24 months. Subjects who discontinue treatment between 12 and 24 months of treatment will be asked to return to the clinic for a 24 month clinical assessment. Subjects who discontinue early from study drug are considered “on study” as long as they continue to return for their clinical assessments at 12 and 24 months as outlined above, at which efficacy (MMSE, CDR, ADAS- cog₁₄) and quality of life (EQ-5D, QOL-AD and Zarit’s Burden Interview) will be assessed along with concomitant medications and AEs. These 12 and 24 month clinical assessment visits do not need to be attended if they fall within 8 days (visit window) after the ED Visit or within ±8 days of either of the Follow-Up Visits (Visit 14 and Visit 15).

^c All subjects, regardless of whether they complete all 24 months of treatment or discontinue study drug prematurely, will complete 2 posttreatment Follow-Up Visits; one 4 weeks after the last dose of study drug and a second 12 weeks after the last dose of study drug (Visit 14 and Visit 15 respectively). If clinically indicated, more frequent safety assessments can be made as UNS assessments or visits during the posttreatment Follow-Up Period. Subjects who have a Grade 2 or greater lymphocytopenia (less than 800/mm³) during the follow-up period (ie, at either Visit 14 or Visit 15) should have ALC measured every 4 weeks until resolution or confirmation of a non drug-related cause of the lymphocytopenia. ALC will be derived from the CBC with differential representing the normal lymphocytes (with atypical lymphocytes removed and presented as a separate count if they are present) and calculated by the white blood cell count × percentage of lymphocytes. (revised per Amendment 01)

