9.7.1.6.1 PRIMARY EFFICACY ANALYSIS

The primary analysis will be based on an intent to treat philosophy without regard to adherence to treatment. The primary analysis of the change from baseline in CDR-SB at 24 months will be performed to compare elenbecestat (E2609) 50 mg per day versus placebo using a linear mixed effects model for repeated measures (MMRM) on the FAS. The MMRM model will include baseline CDR-SB as a covariate, with treatment group, visit, randomization stratification variables (ie, region [7 levels], clinical dementia [yes, no], and concurrent AD medication use at randomization (Visit 2) [yes, no]), and treatment group-by-visit interaction as fixed effects. An unstructured covariance matrix will be employed to model the covariance of within subject effect; if MMRM fails to converge then a covariance structure with fewer parameters from the following list will be employed according to the prespecified order in the list until the MMRM converges. The list of covariance structure will include Heterogeneous Toeplitz, Toeplitz, Heterogeneous Compound Symmetry, and Compound Symmetry. This primary analysis will include all observed post baseline data of the change from baseline in CDR-SB without imputation of missing values. The treatment effect for elenbecestat (E2609) versus placebo will be compared at 24 months based on MMRM model. The LS means and difference in LS means between elenbecestat (E2609) treatment group and placebo, and corresponding 95% CI will be presented.

The null hypothesis is that there is no difference in the mean change from baseline in CDR-SB at 24 months between elenbecestat (E2609) 50 mg per day and placebo. The corresponding alternative hypothesis is that there is a difference in the mean change from baseline in CDR-SB at 24 months between elenbecestat (E2609) 50 mg per day and placebo.

The primary analysis will be repeated to minimize the impact of change in concomitant AD medications where efficacy data after initiation of new AD medications and increase of current AD medications will be censored.

The following sensitivity analysis will be conducted to evaluate the impact of missing data: the primary endpoint will be analyzed using ANCOVA after multiple imputation. The ANCOVA model will include baseline CDR-SB as a covariate, with treatment group and randomization stratification variables as factors.

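### Table 3 note b lets Visit 14 or 15 stand in for a drug stopper's 12- or 24-month return, but those visits do not collect EQ-5D, QOL-AD or Zarit

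*Protocol*

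**What the plan says.** Table 3 in Section 9.5.2.1 and its note b set the schedule for subjects who stop study drug early.

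- **The return visits.** Subjects who stop before month 12 are asked back at 12 and 24 months; those who stop later are asked back at 24 months. Besides MMSE, CDR and ADAS-cog14, note b says that "quality of life (EQ-5D, QOL-AD and Zarit’s Burden Interview) will be assessed along with concomitant medications and AEs".
- **The follow-up visits.** In stoppers these are dated from the last dose: "Follow-Up Visits will be scheduled 4 and 12 weeks after the last dose of study drug (Visit 14 and Visit 15, respectively").
- **The waiver, ED clause.** The return "clinical assessment visits do not need to be attended if they fall within 8 days (visit window) after the ED Visit".
- **The waiver, follow-up clause.** The return is also excused when it lies "within ±8 days of either of the Follow-Up Visits (Visit 14 and Visit 15").
- **What the follow-up visits collect.** Table 3 marks EQ-5D, QOL-AD and the row for the Zarit "Burden Interview of study partner" at Visits 7, 9, 11, 13 and ED. All three rows are blank at Visits 14 and 15. CDR, MMSE, ADAS-cog14 and FAQ are marked at ED, Visit 14 and Visit 15.

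Section 9.7.1.1.3 lists change at 24 months in EQ-5D, QOL-AD and Zarit among the exploratory endpoints. Section 9.7.1.6.3 tests each at a two-sided 0.05 level.

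**The concern.** A waiver of this kind is sound only if the visit that stands in collects what the waived visit would have collected. Here it does not. One sentence of note b requires the three questionnaires, and the next accepts in their place a visit at which none is scheduled. A site that follows the Protocol exactly will not collect them.

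At stake are month-24 values for named exploratory endpoints, and month-12 values of the same instruments. The subjects concerned are all drug stoppers, the group whose later course is hardest to infer from everyone else. An analysis rule can choose among measurements that exist. It cannot supply one that was never taken, so the repair has to be made in the Protocol.

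**Working it through.** **Step 1. Compare content.** All entries are from Table 3 and note b.

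| Measure | Return visit, note b | ED | Visit 14 | Visit 15 |
|---|---|---|---|---|
| CDR, MMSE, ADAS-cog14 | yes | yes | yes | yes |
| FAQ | not listed | yes | yes | yes |
| Concomitant medications, AEs | yes | yes | yes | yes |
| EQ-5D, QOL-AD, Zarit | yes | yes | **no** | **no** |

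The only measures required at the return visit and missing from the substitute are EQ-5D, QOL-AD and Zarit, and only when the substitute is Visit 14 or 15.

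**Step 2. Find who meets the waiver.** Let L be the day of last dose. Visit 14 is on Day L + 28 and Visit 15 on Day L + 84. Month 12 is Day 365 and month 24 is Day 729. The waiver applies if the follow-up visit is within 8 days of the target day.

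- Month 24 through Visit 14: |L + 28 - 729| ≤ 8, so L = 693 to 709 (17 days).
- Month 24 through Visit 15: |L + 84 - 729| ≤ 8, so L = 637 to 653 (17 days).
- Month 12 through Visit 14: |L + 28 - 365| ≤ 8, so L = 329 to 345 (17 days).
- Month 12 through Visit 15: |L + 84 - 365| ≤ 8, so L = 273 to 289 (17 days).

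Each time point has 34 qualifying days out of 728 possible last-dose days: 34/728 = 4.7%.

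**Step 3. Convert to subjects.** The Protocol does not say how many will stop drug. The 30% dropout in Section 9.7.2 is not defined as drug stopping, so a range is used. Assume that stopping is uniform over the 728 days and that those concerned would otherwise return.

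- 20% stop: 1330 × 0.20 × 34/728 = 12.4 subjects (0.9% of those randomized)
- 30% stop: 1330 × 0.30 × 34/728 = 18.6 subjects (1.4%)
- 40% stop: 1330 × 0.40 × 34/728 = 24.8 subjects (1.9%)

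The count at month 12 is the same under these assumptions.

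**Step 4. Bound any effect on the primary endpoint.** First reproduce the planned size from Section 9.7.2. The difference is 0.25 × 1.75 = 0.4375 and the SD is 2.05. Then n per arm = 2 × (1.960 + 1.282)² × 2.05² / 0.4375² = 462, and 462/0.70 = 660, a total of 1320. This agrees with the stated 1330 to within 1%. With 665 × 0.70 = 465.5 evaluable per arm, power is 0.902.

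Now suppose, against Step 1, that every affected month-24 CDR-SB were unusable at 30% stopping. The loss would be 665 × 0.30 × 34/728 = 9.3 per arm, and power would be 0.897.

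**Step 5. Find the nearest questionnaires that do exist.** ED takes place within 7 days of last dose and collects all three.

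- Waived through Visit 14 (L = 693 to 709): ED falls between 729 - 709 - 7 = 13 and 729 - 693 = 36 days before Day 729.
- Waived through Visit 15 (L = 637 to 653): ED falls between 729 - 653 - 7 = 69 and 729 - 637 = 92 days before Day 729.

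**The case against.** The strongest reply is that little is lost. The three measures are exploratory. The same subjects completed them at ED, about 2 to 5 weeks before Day 729 if waived through Visit 14. Those waived at month 12 are still asked back at month 24. The waiver makes attendance unnecessary but does not forbid it. Subjects who leave the study altogether lose nothing through a waived visit, so the counts apply only to stoppers who would have come back.

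All of that stands, and it is why the point is minor. It does not remove the gap. For those waived through Visit 15, the nearest questionnaires are 10 to 13 weeks old. Even for those waived through Visit 14, ED is at least 13 days before Day 729, outside the window in note a ("A window of ±10 days will be permitted for Visit 7 to 13 inclusive").

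A reader might infer three stronger things. The Protocol supports none of them.

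- **That month-24 primary data are lost.** Section 9.7.1.6.1 states that "The treatment effect for elenbecestat (E2609) versus placebo will be compared at 24 months based on MMRM model", and the Table 3 columns for Visits 14 and 15 read months 25 and 27. Those labels describe subjects who complete treatment. In a stopper who meets the waiver, the follow-up CDR is taken within 8 days of Day 365 or 729, inside the ±10-day window for Visits 9 and 13. Assigning it to month 12 or 24 is ordinary content for a statistical analysis plan, which is not shown.
- **That 8 days contradicts the windows in note a.** Note a limits how far a visit may drift. Note b says how near another visit must be to make a second trip unnecessary. These are separate rules; the words in brackets, visit window, are at most a loose label.
- **That the ED part of the waiver also loses data.** It does not, because ED collects all three questionnaires.

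**Conclusion.** The gap is real and narrow. Under note b as written, a drug stopper who uses the follow-up part of the waiver has no EQ-5D, QOL-AD or Zarit at month 12 or month 24. The rule covers 4.7% of stoppers per time point if stopping is uniform over time. At month 24 that is about 12 to 25 of 1330 subjects for 20% to 40% stopping. Both the stopping rates and the uniform pattern are assumptions, and the count also assumes that these subjects would otherwise attend.

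The primary CDR-SB and the MMSE, ADAS-cog14 and FAQ are unaffected. Even the contrary assumption about CDR-SB would move power only from 0.902 to 0.897. Severity is minor: this is a cheap improvement and no threat to the trial's main conclusion.

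**What to change.** Add one sentence to note b: when Visit 14 or Visit 15 takes the place of the 12- or 24-month assessment, EQ-5D, QOL-AD and Zarit's Burden Interview are also administered at that visit. A matching mark with a footnote in the three Table 3 rows would make it visible to sites.

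Keep the 8-day limit. Aligning it with the ±10 days of note a would widen the waiver from 2 × 17 = 34 to 2 × 21 = 42 last-dose days per time point, about 24% more. Without the added questionnaires, that would enlarge the loss.

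The cost is a footnote change and three instruments the trial already uses, at a visit already being attended, for roughly 20 subjects per time point. The study partner must be available for the proxy, self-report and burden questionnaires; Section 9.5.1.6 already allows this by telephone where the investigator finds it suitable.

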9.5.2.2 Description of Procedures/Assessments Schedule

Please refer to [Table 2](#) and [Table 3](#) for the timings of the procedures and assessments to be performed during the study. Screening assessments will be organized into 5 tiers (see [Table 2](#)). See [Section 9.5.1](#) for a full description of the procedures and assessments to be performed during this study.

[Table 4](#) presents the number of blood and CSF samples, and the total volume of blood and CSF that will be collected throughout the study. Additional samples may be taken at the discretion of the investigator if the results of any tests fall outside reference ranges or if clinical symptoms necessitate testing to ensure subject safety.

Table 4 Summary of Blood and CSF Sample Volumes

Assessment	Total Number of Collection Time Points	Sample Volume, Number of Time Points x Volume per Collection (mL)		Total Volume ^a (mL)
		Screening Visits	Treatment and Follow-Up Periods	
Blood				
Clinical chemistry	15	1×5 mL	14×5 mL	75 mL
Serum pregnancy test at Screening (females of child-bearing potential only)	1	can use blood drawn for clinical chemistry	none	no additional volume
Hematology	15	1×2 mL	14×2 mL	30 mL
Thyroid function tests (thyroid stimulating hormone, free triiodothyronine and free thyroxine)	1	1×5 mL	None	5 mL
Viral screen at Screening (Hepatitis B and C)	1	1×5 mL	None	5 mL
Viral characterization at Visit 2 (previous exposure to CMV, HSV1, HSV2, etc.)	1	None	1 x 4 mL	4 mL
Vitamin B12 at Screening	1	1×5mL	None	5 mL
Blood for immunologic assessments, including isolation of PBMCs for storage and later testing	15	1×20 mL	14×20mL	300 mL
Blood for immune status	8	none	8×5 mL	40 mL
PD and exploratory biomarker sample (revised per Amendment 01)	10	1×24 mL	9×12 mL	132 mL
PK analysis	7	none	7×4 mL	28 mL
Pharmacogenomic sample (revised per Amendment 01)	1	1×3 mL	None	3 mL
All blood samples, total volume collected (revised per Amendment 01)		69 mL	558 mL	627 mL
CSF				
Amyloid eligibility	1	1×12 mL	none	12 mL
PD / PK (optional longitudinal substudy)	1	none	1×12 mL	12 mL

CMV = cytomegalovirus, CSF = cerebrospinal fluid, HSV1 = herpes simplex virus 1 (orolabial herpes), HSV2 = herpes simplex virus 2 (genital herpes), PBMCs = peripheral blood mononuclear cells, PD = pharmacodynamics, PK = pharmacokinetic.

a: The total volume includes all blood/CSF collection from Screening through Week 117 (Followup Visit).

9.5.3 Appropriateness of Measurements

All clinical assessments are standard measurements commonly used in studies of AD.

Standard safety assessments incorporated into this protocol include assessment of AEs and SAEs, measurement of vital signs, clinical laboratory assessments, physical examinations (including dermatologic review), neurologic examinations, ECG measurements, assessments of suicidal thinking and behavior, and MRI.

9.5.4 Reporting of Serious Adverse Events, Pregnancy, and Events Associated with Special Situations

9.5.4.1 Reporting of Serious Adverse Events

All SAEs, regardless of their relationship to study treatment, must be reported on a completed SAE form by email or fax as soon as possible but no later than 24 hours from when the investigator becomes aware of the event.

SAEs, regardless of causality assessment, must be collected up to 12 weeks after the last dose of study drug. All SAEs must be followed to resolution or, if resolution is unlikely, to stabilization. Any SAE judged by the investigator to be related to the study treatment or any protocol-required procedure should be reported to the sponsor regardless of the length of time that has passed since study completion.

The detailed contact information for reporting of SAEs is provided in the Investigator Study File.

For urgent safety issues, please ensure all appropriate medical care is administered to the subject and contact the appropriate study team member listed in the Investigator Study File.

It is very important that the SAE report form be filled out as completely as possible at the time of the initial report. This includes the investigator's assessment of causality.

Any follow-up information received on SAEs should be forwarded within 1 business day of its receipt. If the follow-up information changes the investigator's assessment of causality, this should also be noted on the follow-up SAE form.

Preliminary SAE reports should be followed as soon as possible by detailed descriptions including copies of hospital case reports, autopsy reports, and other documents requested by the sponsor.

The investigator must notify his/her IRB/IEC of the occurrence of the SAE in writing, if required by their institution. A copy of this communication must be forwarded to the sponsor, or its designee, to be filed in the sponsor's Trial Master File.

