All subjects who discontinue study drug before reaching 12 months of treatment will also be asked to return to the clinic for a 12-month clinical assessment and then again at 24 months. Subjects who discontinue treatment between 12 and 24 months of treatment will be asked to return to the clinic for a 24 month clinical assessment. Subjects who discontinue early from study drug are considered “on study” as long as they continue to return for their regularly scheduled clinical assessments at 12 and 24 months as outlined above, at which efficacy and quality of life will be assessed along with concomitant medications and AEs. However, subjects who discontinue study drug early are not considered to have ‘completed’ the study as a final Subject Disposition.

The primary reason for discontinuation and all other reason(s) contributing to the subject’s discontinuation from study drug(s) should be collected on the ED from study drug electronic case report form (eCRF) page. In addition, the date of last dose of study drug(s) will be recorded on the Study Drug Dosing eCRF page. If a subject discontinues study treatment and the study at the same time, the end-of-study procedures (Final Visit) will be followed (see [Section 9.5.5](#)).

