9.5.1.5.1 ADVERSE EVENTS AND EVENTS ASSOCIATED WITH SPECIAL SITUATIONS

An AE is any untoward medical occurrence in a subject or clinical investigation subject administered an investigational product. An AE does not necessarily have a causal relationship with the medicinal product. For this study, the study drug is elenbecestat (E2609).

The criteria for identifying AEs in this study are:

- Any unfavorable and unintended sign (including an abnormal laboratory finding), symptom, or disease temporally associated with the use of an investigational product, whether or not considered related to the investigational product (Note: Every sign or symptom should not be listed as a separate AE if the applicable disease [diagnosis] is being reported as an AE)
- Any new disease or exacerbation of an existing disease
- Any deterioration in nonprotocol-required measurements of a laboratory value or other clinical test (eg, ECG or x-ray) that results in symptoms, a change in treatment, or discontinuation of study drug
- Recurrence of an intermittent medical condition (eg, headache) not present pretreatment (Baseline)
- An abnormal laboratory test result should be considered an AE if the identified laboratory abnormality leads to any type of intervention, withdrawal of study drug, or withholding of study drug, whether prescribed in the protocol or not.

All AEs observed during the study will be reported on the eCRF. All AEs, regardless of relationship to study drug or procedure, should be collected beginning from the time the subject signs the study ICF through the last visit (Visit 15, as shown in [Table 3](#)). Subjects who fail screening primarily due to AE(s) must have the AE(s) leading to screen failure reported on the Screening Disposition eCRF and the Adverse Event eCRF. SAEs will be collected for 12 weeks after the last dose.

Abnormal laboratory values should not be listed as separate AEs if they are considered to be part of the clinical syndrome that is being reported as an AE. It is the responsibility of the investigator to review all laboratory findings in all subjects and determine if they constitute an AE. Medical and scientific judgment should be exercised in deciding whether an isolated laboratory abnormality should be classified as an AE. Any laboratory abnormality considered to constitute an AE should be reported on the Adverse Event eCRF.

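### SAE collection stops 12 weeks after the last dose (related SAEs excepted), although early stoppers stay on study with AEs assessed at months 12 and 24

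*Protocol*

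**What the plan says.** Two sections set when collection ends. Section 9.5.4.1 says "SAEs, regardless of causality assessment, must be collected up to 12 weeks after the last dose of study drug". Section 9.5.1.5.1 repeats this for SAEs ("SAEs will be collected for 12 weeks after the last dose") and says that all AEs "should be collected beginning from the time the subject signs the study ICF through the last visit", which it identifies as Visit 15. Section 9.5.4.1 makes one exception: an SAE that the investigator judges related to study treatment or to a protocol procedure is reportable with no time limit.

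Table 3 note c fixes the timing of Visit 15 for everyone, early stoppers included: "a second 12 weeks after the last dose of study drug (Visit 14 and Visit 15 respectively").

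Other sections keep early stoppers in follow-up beyond that visit. Under section 9.3.3, subjects who stop before 12 months "will also be asked to return to the clinic for a 12-month clinical assessment and then again at 24 months"; those who stop between 12 and 24 months are asked back at 24 months. Section 9.5.5 and Table 3 note b say the same and count these subjects as on study while they return. At those visits efficacy and quality of life "will be assessed along with concomitant medications and AEs".

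On the use of the later data, section 9.7.1.6.1 says: "The primary analysis will be based on an intent to treat philosophy without regard to adherence to treatment".

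**The concern.** For a subject who completes treatment, Visit 15 is the last visit, and the two collection rules agree. For an early stopper it is not: there may be one or two later visits at which AEs are assessed. The text does not say whether the AE question at those visits looks back over the gap since Visit 15, or whether an SAE found there is reportable under 9.5.4.1.

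Take a subject who stops at week 12 and has a stroke at month 10 that is judged unrelated. The event lies outside the SAE window but before the month 12 assessment. One site could report it and another could leave it out, and each could cite the protocol.

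The stake is the comparison of all-cause deaths and SAEs by randomised arm over the same period that the primary analysis covers. The gap could also differ between arms. Sections 9.3.3 and 9.5.1.5.5 require drug to be stopped for repeat confirmed lymphocytopenia, moderate or severe hepatic impairment, certain rashes and moderate to severe herpes, and section 7.1 names lymphocyte reductions, drug rash and herpes relapse among the findings of the multiple-dose study. If those risks are real at the study dose, more active-arm subjects would pass out of the SAE window early. The protocol does not establish that they would.

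**Working it through.** **Inputs.** From Table 3: Visit 13 is Day 729 (104 weeks elapsed), Visit 15 is Day 813 (116 weeks elapsed), and month 12 is 52 weeks elapsed. From 9.5.1.5.1 and 9.5.4.1: the SAE window is 12 weeks after the last dose. From 9.3.3 and note b: early stoppers return at months 12 and 24.

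**The plan's own figure.** (813 − 729) / 7 = 84 / 7 = 12.0 weeks. Visit 15 and the SAE window therefore end together.

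**Time outside the window.** Let t be the week of the last dose, for a subject who remains on study to month 24.

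- Off-drug time to month 24: 104 − t weeks
- Time outside the window: max(0, 104 − t − 12) weeks
- Share outside: 1 − 12 / (104 − t) for t below 92

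| Last dose (week) | Window closes (week) | Off-drug weeks to month 24 | Weeks outside window | Share |
|---|---|---|---|---|
| 12 | 24 | 92 | 80 | 87% |
| 26 | 38 | 78 | 66 | 85% |
| 52 | 64 | 52 | 40 | 77% |
| 78 | 90 | 26 | 14 | 54% |
| 80 | 92 | 24 | 12 | 50% |
| 91 | 103 | 13 | 1 | 8% |
| 92 | 104 | 12 | 0 | 0% |

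The share exceeds one half when 104 − t is greater than 24, that is, for stops before week 80. There is no gap for stops from week 92. For a stop at week 12, the 80 weeks divide into 28 weeks before the month 12 visit (weeks 24 to 52) and 52 weeks between the two return visits.

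**Averages, on assumption only.** The protocol gives no distribution of stopping times. If stops were uniform over 0 to 104 weeks, the mean time outside the window would be 92² / (2 × 104) = 40.7 weeks per stopper, and the share of off-drug time would be 92² / 104² = 78%. The share would be 87% if all stops fell in weeks 0 to 26, 59% if all fell in weeks 52 to 104, and 29% if all fell in weeks 78 to 104.

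A subject-year total also needs the number who stop drug and stay on study, which the protocol does not state. With uniform stops, 10% of 1330 (133 subjects) would give 133 × 40.7 / 52.18 = 104 person-years and 30% (399 subjects) would give 311. The upper figure should not be relied on. The only 30% in the protocol is the dropout rate in 9.7.2, which inflates the sample size for subjects expected to have no month 24 value. It is not a count of subjects retained to month 24.

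**After the fix.** If collection ran to the later of 12 weeks after the last dose and the month 24 visit, the time outside the window would be 0 for every t among subjects who stay on study.

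**The case against.** A reader might infer that the protocol lets deaths and SAEs in this period go unrecorded. The text does not support that reading. Section 9.5.1.5.1 says that AEs observed during the study are reported on the eCRF, and returning stoppers are on study. Section 9.5.4.1 opens by requiring every SAE, whatever its relationship, to be reported within 24 hours of awareness. Related SAEs have no time limit. Section 9.5.5 requires a subject who stops attending to be contacted for the reason and for the presence or absence of AEs, so a death would probably come to light. This shows that the text is contradictory, not permissive. It does not close the gap: the contact duty has no schedule, names neither death nor SAEs, and does not lengthen the SAE window. The related-only exception does not serve an arm comparison, which needs events regardless of causality.

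A second objection is that the window is tied to exposure. In the multiple-dose study (section 7.1) lymphocyte effects gradually resolved over 6 to 21 days after the last dose, and 12 weeks is four times the longer figure. Lymphocytopenia, rash and open SAEs are also followed beyond the window. As a rule for attributing events to the drug, this is reasonable. It does not explain why AEs are assessed at months 12 and 24, or which of them count.

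Third, no planned AE table is harmed. Section 9.7.1.8.2 limits the summaries to treatment-emergent events, up to 4 weeks after the last dose. That stands.

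Fourth, the primary analysis does not follow every randomised subject to month 24. Stoppers are only asked to return, the Full Analysis Set needs a postdose measurement, and the model uses observed data. That also stands. The mismatch concerns stoppers who do return, and those who would have returned but died.

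**Conclusion.** The point holds as a conflict between passages that needs reconciling. Apart from related SAEs, the stated rules close collection 12 weeks after the last dose, while other sections keep the same subjects on study with AEs assessed later. How much time is exposed depends on when drug is stopped: most of the off-drug period for stops before about week 80, a shrinking part after that, and none from week 92. These figures are date arithmetic and assume only that the subject remains on study to month 24.

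Three stronger conclusions are not supported: that such events need not be captured at all, that the treatment-emergent tables are compromised, and that a particular number of subject-years is lost. The last rests on an assumed stopping pattern and an assumed retention, neither of which the protocol gives. An imbalance between arms is possible but conditional on the drug's named risks being real. The protocol text at hand is the last of nine parts, so whether another part changes this wording cannot be seen.

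**What to change.** In 9.5.1.5.1 and 9.5.4.1, set the end of collection for early stoppers who remain on study to the later of 12 weeks after the last dose and the last on-study visit (month 24). Apply this at least to SAEs and deaths, regardless of causality, and keep the unlimited reporting of related SAEs. Correct the statement that treats Visit 15 as the last visit, so that it agrees with Table 3 note b.

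State in note b that the month 12 and month 24 return visits ask about SAEs since the previous contact, and that the contact required by 9.5.5 establishes whether the subject is alive. All-cause deaths and SAEs can then be listed by randomised arm for the whole on-study period, separately from the treatment-emergent tables, which need no change.

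The cost is amendment wording and some extra processing of background events in subjects no longer taking drug. No visit is added, and AEs are already asked about at the visits concerned.
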